## 9.2 Randomization

A subject is assigned to the active or control group upon returning her informed consent documentation. Assignment is based on pre-set randomization of small groupings. For example, a card drawn from a deck of nine cards, wherein each card is indicated as either active or control according to a 2:1 ratio (i.e. 6 cards are identified as active and 3 card as control). After a card has been drawn it is removed from the deck. After the ninth subject is assigned to the group corresponding to the ninth card, the nine card deck is re-shuffled and a card is drawn for the tenth subject. This process continues until enrollment is complete. Means equivalent to a card draw may alternately be used.

#### 9.3 Blinding

Subjects will be blinded to their treatment group. As described in 6.6, with the exception of the firmware loaded on the Controller component, the devices used in the active and control groups are identical, so visualization and handling of the device by the subject will not compromise the blinding. The devices in both groups generate an electrical output that is perceived by the subject, which reduces the risk of subjects identifying themselves as in the control group. The device user manual (TR-1131-FORM-12) and subject instructions (TR-1131-FORM-15) have been modified/written to eliminate language that might suggest to a subject that she is one group or the other. Similarly, study personnel will be instructed to avoid use of language that might indicate which group a subject is enrolled.

Randomization as defined in 9.2 is implemented by an individual who does not interact with the subjects. Study staff who interact with the subjects are blinded to the randomization. Note however, that there is a risk that study staff who interact with the subjects may be informed of group assignment based on comments by the subjects during the study (e.g. if the subject

<sup>2 Richardson et al, "Pelvic floor electrical stimulation: A comparison of daily and every-other-day therapy for genuine stress incontinence", Adult Urology, 48(1):110-118, 1996.

describes the stimulation in a way that makes the stimulation identifiable). Such comments would be documented in the subject's Case Report File. This unblinding would have little impact on data integrity as the study personnel is not involved in the reporting of outcome measures.

Study personnel who analyze individual subject data will be blinded to group assignment. For example, baseline and 12th week episodes/day calculations and pad weight measurements will be made for each subject by blinded study personnel. Later, when group analysis is performed, blinding will be necessarily broken due to the unequal enrollment ratio.

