## 4.4 Recruitment Strategies

Appreciating that achieving enrollment targets in a clinical study can be challenged by various factors, including difficulty in identifying qualified candidates and candidates not wanting to participate in a study in which they may be assigned to a control group, Elidah has implemented several strategies to mitigate such challenges including:

- Recruitment using social media allows access to thousands of women from across the US, which additionally encouraging participation from a diverse pool of candidates.
- The active to control enrollment ratio is 2:1, giving subjects a greater chance of being assigned to a group that will realize a clinical benefit.
- Subjects in the control arm will optionally be allowed to pursue 6 weeks of treatment with the active device after completion of the control study requirements. Although the subject may elect to monitor and report her experience with the active device, such data will not be included in the analysis of the primary endpoint.

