## Table 5-1: Schedule of Study Activities/Requirements for Active and Control Groups.

### 5.5 Adherence Assessment

Adherence to the study regimen for the active group requires completion of  $\geq 60\%$  (18) of the treatment sessions prescribed during the first 6 weeks, as determined from review of each subject's Daily Log.

Elidah anticipates that subjects' willingness to continue with a frequent treatment schedule may diminish with time for reasons including:

- The subject achieves meaningful clinical improvement or complete elimination of incontinence symptoms during the early weeks of the study
- The subject believes she is in the control group
- The subject is not achieving clinical improvement and become discouraged with the likelihood of future improvement.

• Change in the subject's schedule and/or lifestyle

Accordingly, the prescribed treatment frequency over the latter half of the study is reduced (see Table 5-1). Correspondingly the minimum number of treatment sessions required for adherence is reduced to 1x/week for weeks 7-9 (33%) and 0x/week for weeks 10-12 (0%).

Further, subjects must complete the Pre-study, Baseline and Post-Study requirements to be considered compliant. If a subject does not adhere to the study requirements they will be asked to provide a reason, which will be documented in the Case Report Form (TR-1131-FORM-10). During data analysis, this information will be reviewed by the Data Safety and Monitoring Board to determine if/how the data should be adjudicated (see 10.5).

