## 10.6 Quality Assurance

- **Training** –The Clinical Director is responsible for ensuring that the study staff can perform the responsibilities they have been assigned. All study staff will be required to complete the NIH Protection of Human Subjects Training before performing any function of the study.
- Quality Control Committee Given to the small scope of the study, a Quality Control Committee will not be utilized. The Clinical Director has responsibility pertaining to maintenance of study quality, and the Data Safety and Monitoring Board exists to ensure appropriate human protection regulations are met and adverse events are appropriately handled.
- Metrics Section 9.5 defines that data analysis and statistical approach used to determine study success. Upon completion of the analysis one or more persons not

involved with the original data analysis will audit the data entry, mathematical calculations and statistically driven conclusions.

• **Protocol Deviations** – Protocol deviations will be documented using Protocol Deviation Log (TR-1131-FORM-8) and retained within the Study Binders. The Clinical Director and/or Data Safety and Monitoring Board will make the determination of whether the impact of the deviation should be considered in subsequent analysis.

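### The control-only offer of the active device (4.4) has no stated owner or timing, so it can reveal treatment arms before the rulings on who enters the primary analysis are made

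*Combined protocol and SAP*

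**What the plan says.** On blinding, section 9.3 makes three separate statements.

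- Allocation: "Randomization as defined in 9.2 is implemented by an individual who does not interact with the subjects".
- Contact staff: "Study staff who interact with the subjects are blinded to the randomization".
- Scoring: "Study personnel who analyze individual subject data will be blinded to group assignment", until the group analysis is done.

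Section 9.3 recognises one leak, namely that contact staff "may be informed of group assignment based on comments by the subjects during the study". It dismisses the consequence: "This unblinding would have little impact on data integrity as the study personnel is not involved in the reporting of outcome measures".

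Section 4.4 says: "Subjects in the control arm will optionally be allowed to pursue 6 weeks of treatment with the active device". The trigger is completion of what the control arm requires. No section names the person who makes the offer, and none ties it to data lock or to the end of the trial.

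Two sections leave decisions about the data to judgement. Section 5.5 says of non-adherent subjects: "During data analysis, this information will be reviewed by the Data Safety and Monitoring Board to determine if/how the data should be adjudicated". Section 10.6 says of protocol deviations: "The Clinical Director and/or Data Safety and Monitoring Board will make the determination of whether the impact of the deviation should be considered" in the later analysis. Under 10.5 the board includes the Clinical Director, who manages the study. The board is nowhere stated to be blinded. Section 9.5 restricts the primary test to adherent subjects, so these rulings settle who is counted.

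**The concern.** To run the optional phase, someone must identify the control women, tell them, and supply an active device. Either the allocation holder contacts subjects, or staff who already contact them learn the arm. Unless the offer is held back in some way that the plan does not describe, one of the two statements in 9.3 gives way. A woman who has met every requirement and receives no offer can be inferred to be active.

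Section 9.3 plays down unblinding because contact staff do not report outcomes. That reasoning does not reach the people who decide whose outcome counts. A woman's responder status already exists when her adherence or deviation is ruled on. If her arm is also known, the ruling can be influenced by both, even without intent. The primary test has about 60 subjects and a one-sided threshold of 0.025, so a single inclusion decision can matter.

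**Working it through.** **Step 1: set the sections side by side.**

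| Question | What the plan gives | Where |
|---|---|---|
| Who knows the arm? | One individual without subject contact | 9.3 |
| Who is offered the active device? | Control subjects only | 4.4 |
| When? | After the control requirements are met; nothing on lock or trial end | 4.4 |
| Who makes the offer? | Not stated | – |
| Who rules on non-adherence, and when? | The board, at the data analysis stage | 5.5 |
| Who rules on deviations, and when? | Clinical Director and/or board; no stage given | 10.6 |
| Are they blinded? | Not stated | 5.5, 10.5, 10.6 |

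On the natural reading the offer comes at each woman's own completion. That precedes the 5.5 rulings and may precede the 10.6 rulings.

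**Step 2: other arm-dependent steps.** The 5.5 session criterion (18 of the 30 sessions prescribed in the first 6 weeks, 60%) is written for the active group. Section 6.6 has the board review the forms of control subjects who report pelvic floor contraction. Section 10.2 requires device return from active subjects only. Each can also show the arm to those who adjudicate.

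**Step 3: reproduce the plan's figure.** The primary test is the one-tailed Fisher exact test. With a of n₁ active and c of n₂ control responders, and r = a + c,

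p = Σ over x ≥ a of C(n₁, x)·C(n₂, r − x) / C(n₁ + n₂, r).

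For the example in 9.5, 24/40 v 5/20, p = 0.0105. The plan states 0.01, so it reproduces.

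**Step 4: sensitivity to one ruling.** The starting counts are assumed, not taken from the plan. They sit just short of the threshold.

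| Table | One-tailed p | p ≤ 0.025? |
|---|---|---|
| 22/40 v 5/20 | 0.0258 | No |
| 22/39 v 5/20 (one active non-responder removed) | 0.0208 | Yes |
| 22/40 v 4/19 (one control responder removed) | 0.0136 | Yes |

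**Step 5: worst-case error.** Take a true null with a common responder rate π. Enumerate all tables with a ~ Bin(40, π) and c ~ Bin(20, π), apply the removal in every trial where such a woman exists, and sum the probability of tables with p ≤ 0.025. The rate of 15% is the control rate assumed in one calculation in 9.1; 25% is the control rate in the 9.5 example.

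| Removal | π = 25% | π = 15% |
|---|---|---|
| None | 1.3% | 0.7% |
| One control responder | 3.3% | 2.5% |
| Up to two control responders | 8.1% | 4.0% |
| One active non-responder | 1.3% | 0.7% |
| Two active non-responders | 1.4% | 0.7% |

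Under the null, inflation comes only from removing control responders. Removing active non-responders hardly moves the error rate, although it can change the result of a particular trial, as step 4 shows.

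**The case against.** The strongest reply is that the plan nowhere says the offer is made woman by woman, or that arms become known before adjudication. An offer held until after lock would fit 4.4 equally well and would disturb nothing in 9.3. This stands as a limit on the claim. A reader might infer that the optional phase cannot be run without breaking 9.3, and the documents do not support that. They are silent on timing and ownership, and the silence is the gap.

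Second, a control who qualifies for the offer has already met the requirements, and the 5.5 session threshold is written for the active group. She has therefore largely met the 5.5 criteria, and a control who failed them may never be offered the device. This also stands. It moves the exposure towards deviation rulings under 10.6 and towards active women whose arm is inferred. It also means that a reader should not conclude that every active woman is revealed by elimination: a woman without an offer may be a control who did not complete.

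Third, one might reason that the randomisation decks let staff deduce the arm of women still on treatment. The nine-card deck is only an example in 9.2. The deduction would need all three controls of a deck to be identified while deck-mates are still on treatment, yet they are enrolled consecutively on the same 12-week schedule. No weight is placed on it.

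Fourth, it is tempting to read 3.3% or 8.1% as the error rate that 4.4 produces. Those figures assume arm-aware removal in every trial that contains a control responder, with a lapse open to adjudication each time. They bound arm-aware exclusion in general. At 15%, removing one control responder gives 2.48%, just inside the nominal 2.5%.

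Finally, a control woman's log and post-study measures are complete before any offer, and 9.3 keeps episode calculations and pad weighing with blinded personnel. That is correct, and it confines the problem to inclusion rulings.

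**Conclusion.** The concern holds in a limited form. Sections 4.4 and 9.3 are not reconciled: a control-only offer needs someone who knows the arm and contacts the subject, and 9.3 provides no such person. Nothing protects the 5.5 and 10.6 rulings from that knowledge. The conclusion rests on the natural, unwritten reading that the offer follows each woman's own completion, and on the absence of any statement that the adjudicators are blinded.

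The exposure is who enters the per-protocol primary test; the measurement of outcomes is not in question. One ruling can turn a near miss into a success at the assumed counts. The error rates in the working are ceilings, and no likely size of bias can be derived from the documents. The plan's worked p-value is unaffected. The change should be made because it costs little and blinding cannot be restored once arms are known.

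**What to change.** Keep the optional phase and amend the wording.

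1. In 4.4, 5.5, 9.3 and 10.6, state that each woman's log score, adherence status and deviation rulings are made blind to arm, recorded and locked before her arm is looked up for the offer.
2. State that the allocation holder, who is already unblinded, makes the offer and ships the device. Contact staff, scorers and board members are not told.
3. Amend 9.3 so that the allocation holder has no contact with a subject until that subject's record is locked.
4. Reconcile the other steps that reveal the arm. Apply the 5.5 session criterion to both arms when classifying adherence for analysis, hold the 6.6 review of control subjects' forms until after the lock, and apply the 10.2 device return to both arms. Without this step, the first three changes do not deliver blind rulings.

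The cost is protocol wording, adjudication that runs on a rolling basis instead of once at the end, and a short wait for control women while their records are locked. The sample size and the primary test do not change.

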### 5.7 Blinding

Subjects will be blinded to the assigned treatment group. The individual(s) performing subject level data analysis will be blinded to the treatment arm. Due to the 2:1 assignment ratio blinding, assignment must be revealed during group analysis. See 9.3 for addition discussion of blinding.

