## 9. STATISTICAL CONSIDERATIONS

#### 9.1 Sample Size and Power Analysis

The study is designed to test the null hypothesis that the treatment group and control group are not different (see 2.3). Specific reference is made to the number of subjects who achieve a  $\geq$ 50% reduction in stress urinary incontinence episodes per day when comparing the final outcome to a baseline measure. Several comparable studies were identified in the literature in which similar " $\geq$ 50% reduction in episodes" metrics were reported. From these, sample-size calculations were performed to provide confidence that sufficient subjects would be enrolled to protect against Type II error. Each of these calculations target 80% power and assume an alpha of 2.5%, a 2:1 treatment to control randomization ratio, and a single-tailed test.

• From Sand *et al*, 48% of subjects in the active group (2 treatments per day) were responders compared to 13% of subjects in a control (sham) group. Using these values in a chi-squared sample size calculation one finds that the treatment group for the proposed study needs to enroll 31 subjects.

<sup>1 Sand et al, "Pelvic floor electrical stimulation in the treatment of genuine stress incontinence: A multi-center, placebocontrolled trial", Am J Obstet Cycecol, 173(1):72-79, July 1995.

- From Richardson *et al*, 62% and 73% of subjects (1 treatment/day and 1 treatment every other day) were responders. This study makes reference to the response rate for the sham group in the Sand et al study (13%). Using the 62% and 13% values in a chi-squared sample size calculation one finds that the treatment group for the proposed study should include 16 subjects.
- From a similar, ongoing study in which Elidah is also the Investigator (WIRB-20162650), to date, 71% of subjects are responders. Conservatively estimating the control responder rate at 15% (about the average rate reported in the AHRQ meta-analysis for the control groups in studies using vaginal EMS, Table F97), using a chi-squared sample size calculation one finds that the treatment group for the proposed study needs to enroll 12 subjects.

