## 9.4 Interim Analyses and Stopping Rules

The study will include an interim analyses after 30 and 45 subjects have completed enrollment. The Hyabittle-Peto method will be used determine whether the study should be stopped due to extreme differences between the active and control groups. At either interim analysis if the p-value for the primary efficacy outcome is <0.0013 the study will be determined to have met the endpoint.

In the event of a serious adverse event related to the device/treatment the study will be halted until the safety issue can be addressed (see 7). Due to the small enrollment size, a pre-specified number of adverse events will not be used to trigger an interim analysis or early end to the study.

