## 10.5 Data and Safety Monitoring Plan

Elidah will identify a Clinical Director who will be responsible for managing the study and ensuring that the rights and well-being of human subjects are protected, that the reported data are accurate and complete and verifiable from source documents, and that the conduct of the trial is in compliance with the approved protocol, with good clinical practice, and with applicable regulatory requirements. Specific responsibilities of the Clinical Director include:

- Verify that equipment and staff are adequate to safely and properly conduct the study
- Verify that subjects:
  - Meet eligibility requirements
  - Provided informed consent prior to enrollment
  - Are adequately informed about the device use, study requirements and risks of participation
  - Receive all necessary study materials
  - Return all the required data collection forms and specimens
- Verify that, with respect to the device:
  - That shelf-life and storage conditions meet requirements (as applicable)
  - Sufficient supplies (i.e. electrodes, controllers) are sufficient to complete the study
  - That the device is provided only to eligible subjects
  - That the receipt, use, and return of the device is controlled and complies with applicable regulation.
- Verify that source documents and data analyses are accurate and complete
- Verify that adverse events are appropriately reported
- Verify that protocol deviations are appropriately reported

In addition, a Data Safety and Monitoring Board will be established which will review study compliance and adverse events. The Data Safety and Monitoring Board will comprise, at a minimum, the Clinical Director, an individual responsible for technological aspects of the device and an individual with medical training relevant to the used of the device.

Currently, EMS and TENS devices are sold over the counter and used in an at-home environment. Given the high degree of similarity between those devices and the Elitone device, the described level of monitoring is considered appropriate for the low level of risk (see 7).

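### Two interim looks break the blind by the plan's own rule, and nothing keeps the results from those who decide which subjects count in the primary test

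*Combined protocol and SAP*

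**What the plan says.** **Blinding.** Section 5.7 states that "assignment must be revealed during group analysis", and 9.3 repeats it: "Later, when group analysis is performed, blinding will be necessarily broken due to the unequal enrollment ratio". Section 9.3 also keeps the staff who compute individual outcomes blinded, and has the randomisation implemented by a person who does not deal with subjects.

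**Interim looks.** Section 9.4: "The study will include an interim analyses after 30 and 45 subjects have completed enrollment". At either look, "if the p-value for the primary efficacy outcome is <0.0013 the study will be determined to have met the endpoint". No analyst is named, and no limit is placed on who sees the results.

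**Who counts.** The primary analysis in 9.5 uses adherent subjects only; an intent-to-treat version is optional. For subjects who do not adhere, 5.5 says that during data analysis "this information will be reviewed by the Data Safety and Monitoring Board to determine if/how the data should be adjudicated". Section 10.5: "The Data Safety and Monitoring Board will comprise, at a minimum, the Clinical Director", together with a person responsible for the device technology and a person with relevant medical training. Its stated remit there is compliance and adverse events. Section 10.6 leaves it to the Clinical Director and/or the board to decide whether a protocol deviation is taken into account in the analysis.

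**The concern.** If the between-arm comparison were made once, after every subject had been scored and ruled on, breaking the blind at that point would do no harm. Section 9.4 places two between-arm comparisons before the end. By the rule in 5.7 and 9.3, assignments are revealed at each, while decisions on inclusion are still to come.

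Those decisions are discretionary. Section 5.5 gives no criteria for adjudication, and 10.6 gives none for deviations. The people who make them are not barred from knowing the interim result or the arms of subjects already analysed. In a per-protocol test on about 60 subjects, exclusions made with that knowledge would leave the primary result open to challenge, whether or not anyone acted on it. Sections 6.7 and 9.6 say the trial is meant to support regulatory review.

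**Working it through.** **1. Are the looks group analyses?** Section 9.4 compares a p-value for the primary efficacy outcome with 0.0013. Under 9.5 that p-value comes from comparing responders between arms. Each look is therefore a group analysis in the sense of 5.7 and 9.3. The boundary itself is standard: 1 − Φ(3) = 0.00135, against the stated 0.0013.

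**2. How many subjects are left after each look?**

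| Look | Of target 60 | Of 70–80 (9.1) |
|---|---|---|
| 30 | 60 − 30 = 30 | 40–50 |
| 45 | 60 − 45 = 15 | 25–35 |

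Section 9.4 does not say whether its trigger means subjects enrolled or subjects with 12-week outcomes. On either reading, later subjects remain.

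**3. Is the trial likely to continue past both looks?** Exact binomial enumeration, assuming complete outcomes and exact 2:1 splits (20:10, then 30:15), with one-sided Fisher p<0.0013 to stop. The rates are those in 9.1, for example "48% of subjects in the active group (2 treatments per day) were responders compared to 13% of subjects in a control (sham) group".

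| Active v control rate | Stop at look 1 | Stop at look 2 | Continue past both |
|---|---|---|---|
| 48% v 13% | 0.0292 | 0.1247 | 1 − 0.0292 − 0.1247 = 0.846 |
| 60% v 25% | 0.0516 | 0.0919 | 0.857 |
| 62% v 13% | 0.1897 | 0.2989 | 0.511 |
| 71% v 15% | 0.3520 | 0.3223 | 0.326 |

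Continuing after the blind has been broken is thus an ordinary outcome, at between 33% and 86%.

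**4. Which decisions are still open to judgement?**
- Scoring: 9.5 takes the first and last 5 log entries, applies fixed arithmetic and a fixed 50% cut, and 9.3 blinds the scorer. Little discretion remains.
- Adherence: the session threshold in 5.5 is stated for the active group only, so applying it as written requires knowing the arm. What happens to non-adherent data is left to the board.
- Deviations: left to the Clinical Director and/or the board (10.6).
- Separately, 6.6 has the board review the case report forms of control subjects who report pelvic floor contraction, which also requires knowing the arm.

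**5. How sensitive is the final test?** One-sided Fisher with x of n₁ active and y of n₂ control responders, r = x + y: p = Σ over k ≥ x of C(n₁,k)·C(n₂,r−k)/C(n₁+n₂,r). Success requires p ≤ 0.025 (9.5).

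| Active | Control | p | Result |
|---|---|---|---|
| 24/40 | 5/20 | 0.0105 | succeeds (the plan's example, stated as 0.01) |
| 22/40 | 5/20 | 0.0258 | fails |
| 24/40 | 6/20 | 0.0269 | fails |
| 24/40 | 5/19 | 0.0154 | succeeds (one control responder excluded from the row above) |

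The last two rows differ by one exclusion. They were chosen at the boundary. Over the whole sampling distribution at 40 v 20, the chance that excluding one control responder would turn failure into success is about 9% (48% v 13%), 10% (60% v 25%), 2% (62% v 13%) and 1% (71% v 15%).

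**The case against.** The strongest reply is that the plan already protects the outcome. Subjects are blinded and record their own episodes, missing log entries have a fixed rule, and scorers are blinded. The word order in 9.3 also implies that individual calculation comes before group analysis. All of that stands, and it disposes of two stronger readings.

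- A reader might infer that the staff unblinded at a look go on to score later logs. The documents do not say so: the blinding of individual-level scorers in 9.3 is a standing rule, and nothing suspends it after a look. That the looks are run by sponsor staff is itself an inference from the absence of any named outside party.
- A reader might infer that a look discloses the arms of subjects still to come. It discloses only those in the look, apart from some predictability within an unfinished block. With the example deck of nine in 9.2, the 30th subject is third in a block (30 = 3×9 + 3) and the 45th closes one (45 = 5×9).

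It can also be said that one subject can flip any small Fisher test near its threshold, with or without interim looks. That is correct, and it limits what the p-values above can show.

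The audit in 10.6 does not close the gap. It takes place after the analysis and covers data entry, calculations and conclusions, not whether inclusion was decided blind. The reply leaves adherence adjudication and deviation rulings untouched.

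**Conclusion.** The concern holds for inclusion decisions, and not for scoring. Followed as written, the plan reveals assignment at two looks before the trial ends, does not restrict the interim results, and leaves inclusion in a per-protocol primary test to the discretion of a board that includes the Clinical Director. Those rulings can be made knowing the interim trend and the arms of subjects already in a look.

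The exposure covers up to 30 of the target 60 subjects after the first look and 15 after the second, plus any ruling not yet settled for subjects already analysed. Near the threshold, one or two subjects can decide the result. The Fisher values illustrate that sensitivity. They do not measure bias, and nothing in the documents allows bias to be estimated or suggests that it is intended. The continuation probabilities rest on complete outcomes and exact 2:1 splits at each look.

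The break is also not forced by the 2:1 ratio. Unequal allocation makes the arms recognisable to whoever runs the test; it does not require adjudicators to see them.

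**What to change.** Amend 5.5, 9.3, 9.4 and 10.6 as follows.

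- In 9.3, delete *necessarily*. State that each subject's responder status, adherence decision and deviation decisions are finalised and locked without arm labels before her data enter any interim or final group analysis. For this to work, 5.5 must give an adherence criterion for the analysis that can be applied without knowing the arm.
- In 9.4, name by role an existing person who runs a pre-written Fisher test and who neither scores, adjudicates nor makes the remaining assignments. The person drawing cards under 9.2 should not do it while draws remain, because the allocator would then know the trend. Alternatively, generate the full allocation list in advance, so that whoever holds it cannot influence later assignments.
- Release only stop or continue to the Clinical Director, the board and study staff until final lock.
- Hold the board's arm-specific review under 6.6 until that subject's inclusion decisions are locked.

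The cost is some protocol wording, a short script and a little procedural work. Sample size, endpoint and alpha are unchanged. The sponsor gives up sight of interim response rates.
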